7.1.3 Secondary endpoint(s)

Quantitative data:

Quantitative variables will be summarized by number of patients, mean, median, standard deviation, minimum, and maximum for each time point. Changes from baseline will also be calculated and tabulated for each time-point (D35-D0 and D84-D0).

A mixed ANOVA model (PROC MIXED) for repeated measures will be fitted to raw data, including the factor treatment as fixed (2 levels), time as fixed (3 levels), and product by time interaction, as well as the patient effect as random.

From this model, the contrasts of interest will be built on the adjusted means:

- * to test whether each change from baseline (D35-D0 and D84-D0) differ significantly from 0 by product.
- * to test whether the products differ significantly for each change from baseline (D35-D0 and

D84-D0).

The underlying assumptions (normality and homoscedasticity) will be checked using Shapiro-Wilk test and graphical representations of the residuals. In case of strong deviation, a non-parametric approach will be performed.

Qualitative data:

Categorical variables will be summarized with frequency and percentages for each time point.

For the global performance, treatments groups will be compared with a Chi2 test.

For other qualitative variables, the changes from baseline for each product will be assessed with a Wilcoxon signed-rank test. The comparison between the treatments will be assessed with a Mann-Whitney test for each change from baseline (D35-D0 and D84-D0).

Safety data:

The safety data will be summarised using descriptive statistics by treatment group in the Safety population.

Summary safety assessments include AEs, best-corrected visual acuity, ocular symptoms and the global tolerance assessment by the investigator.

The adverse events will be coded using the MedDRA dictionary. The evaluation of the adverse events only considers the treatment-emergent AEs (TEAEs) with onset date on or after the day of the first study drug instillation.

The ocular TEAEs and the non-ocular TEAEs will be analysed separately.

The number and percentage of patients experiencing at least one AE will be provided by treatment group, by primary SOC and PT, for the following categories of events:

- All AEs
- All TEAEs
- Maximum severity for all events by PT (regardless of causality)
- Treatment-related AEs
- Serious AEs
- AEs that lead to study withdrawal.

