4.1.2 Secondary efficacy endpoints

The secondary efficacy endpoints are described below.

- For the parameters hereafter: Oxford total score on worse eye, OSDI total score, Van Bijsterveld total score, Schirmer test result on worse eye, TBUT total score on worse eye, all ocular dryness symptoms score separately and then globally (total score):
 - For each product, description of the parameter at D0, D35 and D84
 - For each product, description of the change of the parameter for each time-point (D35-D0 and D84-D0)
 - For each product, comparison of the change of the parameter at D35 versus D84
 - Comparison of the change of the parameter between products at D35 and then at D84.
- For the parameters hereafter: OSDI in class, evaluation of performance by the patient, evaluation of performance for the investigator and frequency of use of the product:
 - The parameter will be described at D0, D35 and D84 (with frequency and percentage)
 - A comparison of the parameter between products at D0, D35 and D84 will be performed.

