4.3 Derived variables

Source data	Derivation rule	Label	Format
Date of last use of study product, date of D0 visit	TRT_DUR_D=Date of last use of study product – date of D0 visit +1	Treatment duration in days	Numeric
Date of end of study, date of selection visit	STUDY_DUR_D=Date of end of study – date of selection visit +1	Study duration in days	Numeric
OSDI total score	IF 0<=OSDI total score < 13 THEN OSDI_CL_D=1 IF 13<= OSDI total score < 23 THEN OSDI_CL_D=2 IF 23<= OSDI total score < 33 THEN OSDI_CL_D=3 IF 33<= OSDI total score < 100 THEN OSDI_CL_D=4	OSDI score in class	1 = "OSDI none" 2 = "OSDI Mild" 3 = "OSDI moderate" 4 = "OSDI severe"
Total Oxford score of the examined eye (i.e. worse eye defined at D0) at day 0, Total Oxford score of the corresponding eye at day 35 (i.e. day 84)	EVOL_OX_D0D35 (i.e. D84) = Total Oxford score of the examined eye (i.e. worse eye defined at D0) at day 35 (i.e. day 84) - Total Oxford score of the corresponding eye at day 0	Change of the Oxford total score from baseline to day 35 (i.e. day 84)	Numeric
Same derivation rule as above for changes on OSDI total score, Van Bijsterveld total score, Schirmer test result, TBUT total score, all ocular dryness symptoms score from D0 to D35 and from D0 to D84.			

Total Oxford score of the examined eye (i.e. worse eye defined at D0) at day 0, Total Oxford score of the corresponding eye at day 35 (i.e. day 84)	EVOL_OXREL_D0D35 (i.e. D84) = (Total Oxford score of the examined eye (i.e. worse eye defined at D0) at day 35 (i.e. day 84) - Total Oxford score of the corresponding eye at day 0) / Total Oxford score of the corresponding eye at day 0	Relative change of the Oxford total score from baseline to day 35 (i.e. day 84) in percentage	Numeric
Same derivation rule as above for changes (relative variation) on OSDI total score, Van Bijsterveld total score, Schirmer test result, TBUT total score, all ocular dryness symptoms score from D0 to D35 and from D0 to D84.			
Adverse Event	IF at least one adverse event is reported for the patient, ALO_AE=1 ELSE, ALO_AE=0	At least one AE	0 = "No" 1 = "Yes"
Same derivation rule as above for at least one TEAE, at least one severe AE, at least one AE related to the treatment, at least one SAE, at least one AE that lead to study withdrawal			

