5.3 Changes to statistical information in the clinical trial protocol

Not applicable.

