7.6.2 Secondary efficacy endpoint

- For the parameters hereafter: Oxford total score on worse eye, OSDI total score, Van Bijsterveld total score, Schirmer test result on worse eye, TBUT total score on worse eye, all ocular dryness symptoms score separately and then globally (total score):
 - For each product, description of the parameter at D0, D35 and D84.
 - For each product, description of the change of the parameter for each time-point (D35-D0 and D84-D0, relative and absolute variation).
 - A mixed ANOVA model (PROC MIXED) for repeated measures will be fitted to raw data, including the factor treatment as fixed (2 levels), time as fixed (3 levels: D0, D35 and D84), and product by time interaction, as well as the patient effect as random. From this model, the contrasts of interest will be built on the adjusted means:
 - To test whether each change from baseline (D35-D0 and D84-D0) differ significantly from 0 by product.
 - To test whether the products differ significantly for each change from baseline (D35-D0 and D84-D0).
 - The underlying assumptions (normality and homoscedasticity) will be checked using Shapiro-Wilk test and graphical representations of the residuals. In case of strong deviation, a non-parametric approach will be performed.
- For OSDI parameter, the different scores will be classified into the following categories:
 - OSDI None: OSDI (0 - <13)
 - OSDI Mild: OSDI (13 - <23)
 - OSDI Moderate: OSDI (23 - <33)
 - OSDI Severe: OSDI (33 - <100)

The parameter will be described at D0, D35 and D84 (with frequency and percentage)

A comparison of the different categories between products at D0, D35 and D84 will be performed, treatments groups will be compared with a Chi2 test.

- For the parameters hereafter: evaluation of performance by the patient, evaluation of performance for the investigator and frequency of use of the product:
 - The parameter will be described at D0, D35 and D84 (with frequency and percentage)
 - A comparison of the parameter between products at D35 and D84 will be performed: for the evaluation of performance by the patient and by the investigator, and for

frequency of use of the products, treatments groups will be compared with a Chi2 test.

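### SAP 7.6.2 adds an ordered OSDI class and compares it between products with a Chi2 that ignores the order, departing without declaration from the protocol's rule for qualitative variables (minor)

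*SAP*

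**What the plan says.** **Protocol.** Sections 1.5 and 6.1.3.2 list the OSDI score as a secondary endpoint; neither mentions OSDI classes. Under qualitative data, section 7.1.3 assigns Chi2 to one variable: "For the global performance, treatments groups will be compared with a Chi2 test". It then sets a residual rule. Within product: "For other qualitative variables, the changes from baseline for each product will be assessed with a Wilcoxon signed-rank test". Between products: "The comparison between the treatments will be assessed with a Mann-Whitney test for each change from baseline (D35-D0 and D84-D0").

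**SAP.** Section 4.3 derives the class as a code from 1 (none) to 4 (severe), for example "IF 13<= OSDI total score < 23 THEN OSDI_CL_D=2". Section 4.1.2 plans the between-product look visit by visit: "A comparison of the parameter between products at D0, D35 and D84 will be performed". Section 7.6.2 names the test: "A comparison of the different categories between products at D0, D35 and D84 will be performed, treatments groups will be compared with a Chi2 test". No change in class, Mann-Whitney test or signed-rank test is planned for it. Section 7.1.2 puts secondary criteria on both ITT and PP. Section 5.3, headed "Changes to statistical information in the clinical trial protocol", reads "Not applicable".

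**The concern.** The protocol's split has a logic. The performance rating is collected only at D35 and D84, so it has no baseline and a test at the visit is natural. OSDI is collected at D0, D35 and D84, so a class derived from it can be referred to baseline, and its levels are ordered.

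The SAP treats OSDI class like the performance rating. A Pearson Chi2 on four classes has 3 degrees of freedom and gives the same answer whatever the order of the columns. It therefore spends power on patterns that are neither better nor worse. The D0 test examines only chance imbalance between randomised arms. Entry requires OSDI of at least 18, so the lowest class should be empty at that visit.

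Two things are at stake: an avoidable loss of power in a planned output, and a record that says nothing changed when a variable was added and a different test chosen. A non-significant class result could also sit beside a significant OSDI score result and puzzle the reader.

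**Working it through.** **1. The plan's own figure.** The documents give no power or sample size for OSDI class. The only stated size is for the primary test: margin 2, SD 2.5, 90% power, two-sided 95% CI. The normal formula gives n per arm = 2 × (1.960 + 1.282)² × 2.5² / 2² = 32.8, so 33. The noncentral-t version gives power 0.893 at 33 and 0.9015 at 34, hence 34 per arm and 68 in total. Then 68 / 0.85 = 80. This reproduces and is not in dispute. I use 34 per arm below.

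**2. Chi2 ignores order.** Illustrative counts, 40 per arm, none/mild/moderate/severe: 4/8/10/18 against 10/12/9/9. Column totals are 14, 20, 19 and 27, so expected counts per arm are 7, 10, 9.5 and 13.5.

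Chi2 = 2 × (3²/7 + 2²/10 + 0.5²/9.5 + 4.5²/13.5) = 2 × (1.286 + 0.400 + 0.026 + 1.500) = 6.42 on 3 df, p = 0.093.

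Shuffling the class labels leaves this unchanged. Mann-Whitney on the ordered classes gives p = 0.012, and 0.97 after the same shuffle.

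**3. Power under assumed OSDI inputs.** The documents give no OSDI SD or correlation, so these are assumptions: D0 normal with SD 18, truncated at 18 or above (the entry limit); D0 mean 40 with mean fall 15, or D0 mean 33 with mean fall 10; true product difference 10 points; two-sided 5%; classes cut at 13, 23 and 33. The table shows power (%) at one visit, 34 per arm.

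| D0 mean | Correlation | Chi2 at visit | Mann-Whitney, visit class | Mann-Whitney, class change | Wilcoxon stratified by D0 class |
|---|---|---|---|---|---|
| 40 | 0.3 | 39 | 55 | 52 | 55 |
| 40 | 0.5 | 41 | 57 | 58 | 59 |
| 40 | 0.7 | 45 | 61 | 69 | 69 |
| 33 | 0.3 | 39 | 57 | 52 | 55 |
| 33 | 0.5 | 41 | 58 | 57 | 61 |
| 33 | 0.7 | 46 | 64 | 71 | 71 |

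The stratified column comes from 3,000 replicates and the others from 2,000. The Monte Carlo standard error at 2,000 is at most √(0.25/2000) = 1.1 points, and repeat runs moved entries by up to about 3 points. Across runs the ranges are about 40 to 47% for Chi2, 56 to 64% for Mann-Whitney on visit class and 50 to 71% for Mann-Whitney on class change. Null rejection was about 4 to 6% for every test.

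**4. Where the gain comes from.**
- Order (visit-class Mann-Whitney minus Chi2): 16, 16, 16 points at D0 mean 40; 18, 17, 18 at D0 mean 33.
- Reference to D0 (class change minus visit class): −3, +1, +8 points; −5, −1, +7.

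The order gain is steady. The D0 gain appears only at 0.7, and change scores lose a little at 0.3.

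**5. Other inputs.** With D0 mean/SD of 35/15 or 45/18 and correlation 0.4 to 0.8, Chi2 has power 0.37 to 0.65 and class-change Mann-Whitney 0.54 to 0.92 at 34 per arm. Chi2 was lower in every setting. Expected counts below 5 were common (24 to 99% of runs with no difference), yet null rejection stayed at 4 to 6%, so I make no validity point of them.

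**The case against.** The strongest reply is that little depends on this table.

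- **The protocol specified no OSDI-class result.** A reader might infer that the SAP replaced a named protocol analysis. The documents do not support that: the classes first appear in the SAP, and the protocol's rule reaches them only through its general wording. What stands is that the variable and its test are both undeclared.
- **The named OSDI endpoint is intact.** A reader might infer that a real OSDI difference would be missed, or that the within-product test is gone. SAP 7.6.2 fits a repeated-measures mixed model to the OSDI total score, with contrasts on D35-D0 and D84-D0 within and between products. A t-test on score change, as a simple stand-in for that contrast, has power 49, 60 and 80% (D0 mean 40) or 50, 62 and 82% (D0 mean 33) at correlations 0.3, 0.5 and 0.7.
- **Ignoring D0 is not a bias.** A reader might infer that chance imbalance at D0 passes undiluted into the D35 and D84 class tests. At those correlations and D0 mean 40, D0 class correlates only 0.16, 0.29 and 0.44 with visit class. It correlates −0.33, −0.24 and −0.10 with class change, so at 0.3 the change score carries more of the imbalance, in the opposite direction. Randomisation keeps type I error near 5% either way.

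All three replies stand, and they set the weight of the point. None of them justifies an order-blind test on ordered classes or the entry in SAP 5.3.

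**Conclusion.** The point holds as a minor one. For a variable that the SAP itself added, the plan uses a test that discards the class order and differs from the protocol's general rule, and SAP 5.3 records neither fact. The cost is power: about 40 to 47% for Chi2 against about 50 to 71% for ordered tests, at 34 per arm with a 10-point OSDI difference and a correlation of 0.3 to 0.7. Those inputs are assumptions, so the figures show direction and rough size only. Most of the loss comes from ignoring order. The primary ANCOVA, the sample size, the safety analysis and the OSDI score analysis are untouched.

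**What to change.** Before unblinding:

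1. In SAP 7.6.2 and 4.1.2, replace the D35 and D84 Chi2 tests on OSDI class with an ordered test. Either use the protocol's Mann-Whitney on class change between products with signed-rank within product, or use a Wilcoxon (van Elteren) test of visit class stratified by D0 class.
2. Describe the D0 classes without a test, and keep the frequency tables.
3. In SAP 5.3, record OSDI class as an added variable, along with any test that differs from the protocol's.
4. Label the class analysis as supportive of the OSDI score analysis.

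The cost is a few lines of SAP text and a different SAS procedure. Each option has a drawback. Class change counts every one-class shift as equal, and patients who start in the top class (about 73% under the D0 mean 40 assumption) cannot worsen. The stratified test avoids the equal-shift problem but departs from the protocol and must be declared.

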7.7 Safety Analysis

The safety data will be summarised using descriptive statistics by treatment group in the Safety population. Summary safety assessments include AEs.

7.7.1 Adverse events

The adverse events will be coded using the MedDRA dictionary. All Adverse events will be presented by System Organ Class and Preferred Term.

Treatment-emergent AEs (TEAEs) will be defined as AEs with onset date on or after the first day of the study product instillation. If the AE onset date is not available, AEs will be considered as TEAEs by default.

The number and percentage of patients experiencing at least one AE will be provided by treatment group, by primary SOC and PT, for the following categories of events:

- All AEs
- All TEAEs
- Maximum severity for all events by PT (regardless of causality)
- Treatment-related AEs
- Serious AEs
- AEs that lead to study withdrawal.

The difference between treatments groups on the incidence rate will be analysed for each PT using Fisher's exact test.

The statistical significance level of 5% will be applied for the safety analyses.

Will be described globally and by treatment groups (the ocular TEAEs and the non-ocular TEAEs will be analysed separately):

Total number of AEs:

- All AEs
- All TEAEs
- All AEs by severity
- AEs by relationship to the treatment
- AEs by seriousness criterion
- AEs that lead to study withdrawal.

Number and percentage of patients who has presented at least one AE:

- At least one AE
- At least one TEAE
- At least one severe AE
- At least one AE related to the treatment
- At least one SAE
- At least one AE that lead to study withdrawal.

The difference between treatments groups on the incidence rate will be analysed for each PT using Fisher's exact test.

The statistical significance level of 5% will be applied for the safety analyses.

An individual data listing of all AEs will be given. With following information: centre number / patient number / treatment group / inclusion date (D0) / age / sex / AE number / AE description / SOC / PT / Time of occurrence* / Duration** (start date / end date) / severity / picture of clinical signs / Actions taken / Seriousness criterion / timeframe from the last product use-application / relationship with the study product / relationship with the study method / outcome / comments.

The same listing will be produced for SAEs.

* Time of occurrence will be derived in days as follow: inclusion date (D0) – AE start date

** duration in days will be derived as follow: end date – start date +1

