6.4 PROCEDURES

6.4.1 Description of all the clinical-investigation-related procedures that patients undergo during the clinical investigation

Selection visit (D-14 to D -7)

- The ophthalmologist will propose to his/her patient to participate to the clinical investigation.
- Information of the patient on study aims and schedule.
- Signature of information sheet and consent form in two copies by the patient and the investigator.
- Collection of previous medical and ophthalmological history, previous and actual treatments, demographic data.
- The ophthalmologist will evaluate the Ocular Surface Disease Index, the global ocular staining (Oxford score) and will realize the Schirmer test and TBUT.
- Checking of inclusion and exclusion criteria.
- If the patient is eligible, distribution of Hydrabak® to be used three times per day in both eyes until the inclusion visit, as well as a daily log to write eventual concomitant treatments and adverse events.

Inclusion visit (D0)

- The patient will bring back the Hydrabak® and the daily-log completed.
- Collection of adverse events and concomitant treatments.
- The ophthalmologist will evaluate the Ocular Surface Disease Index, the global ocular staining (Oxford score) and will realize Schirmer test and TBUT.
- Checking of inclusion and exclusion criteria.
- If the patient is eligible, inclusion of the patient and attribution of a randomization number.
- The ophthalmologist will evaluate the Van Bijsterveld score.
- The patient will evaluate his/her ocular symptoms.
- A third person will distribute the treatment according to the randomization list and explain the mode of use of the treatment, as well as a daily log to write eventual concomitant treatments and adverse events

D35

- The patient will bring back the treatments (used and non-used) and the daily-log completed.

- Collection of adverse events and concomitant treatments.
- The ophthalmologist will evaluate the Ocular Surface Disease Index, the global ocular staining (Oxford score), the Van Bijsterveld score and will realize Schirmer test and TBUT.
- The patient will evaluate his/her ocular symptoms.
- The patient and the investigator will evaluate the treatment performance on a 4-point scale.
- A third person will distribute the treatment according to the randomization list and remain the patient about the mode of use, as well as a daily log to write eventual concomitant treatments and adverse events.

D84

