4.2 Safety assessments

The safety data will be summarised using descriptive statistics by treatment group in the Safety population.

Summary safety assessments include AEs, best-corrected visual acuity, ocular symptoms and the global tolerance assessment by the investigator.

The adverse events will be coded using the MedDRA dictionary (Version 19.1). The evaluation of the adverse events only considers the treatment-emergent AEs (TEAEs) with onset date on or after the day of the first study drug instillation.

The ocular TEAEs and the non-ocular TEAEs will be analysed separately.

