Evaluation of performance by the investigator at D0, D35 and D84 by treatment groups – PP population

Evaluation of performance by the investigator at D0, D35 and D84 by treatment groups – ITT population

Frequency of use of the product at D0, D35 and D84 by treatment groups – PP population

Frequency of use of the product at D0, D35 and D84 by treatment groups – ITT population

AEs by SOC, PT and by treatment groups – Safety Population
TEAEs by SOC, PT and by treatment groups – Safety Population
Severe AEs by SOC, PT and by treatment groups – Safety Population
Treatment-related AEs by SOC, PT and by treatment groups – Safety Population
Serious AEs by SOC, PT and by treatment groups – Safety Population
AEs that lead to study withdrawal by SOC, PT and by treatment groups – Safety Population

AEs by severity and treatment groups
AEs by relationship to the treatment and treatment groups
AEs by seriousness criterion and treatment groups

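### The plan says only TEAEs are evaluated, but the by-arm severity and serious AE summaries have no onset limit and the Fisher test names no event set

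*SAP*

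**What the plan says.** **The rule.** SAP 4.2 says the AE evaluation "only considers the treatment-emergent AEs (TEAEs) with onset date on or after the day of the first study drug instillation". Protocol 7.1.3 (safety data) has the same rule.

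**The tables.** SAP 7.7.1 says "The number and percentage of patients experiencing at least one AE will be provided by treatment group, by primary SOC and PT" and lists six categories. All AEs and all TEAEs are separate entries. The severity entry reads "Maximum severity for all events by PT (regardless of causality". Treatment-related, serious and withdrawal AEs follow with no onset condition. Protocol 7.1.3 has the same list.

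**The flags.** SAP 4.3 sets the basic flag by "IF at least one adverse event is reported for the patient, ALO_AE=1", and continues "Same derivation rule as above for at least one TEAE, at least one severe AE, at least one AE related to the treatment", then serious AEs and AEs leading to withdrawal. No onset date enters the rule.

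**The planned outputs.** SAP 9.1 has six SOC/PT tables by arm. One is titled for TEAEs and five for AEs, among them "Serious AEs by SOC, PT and by treatment groups".

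**The test.** Protocol 7.1.3 and SAP 7.7.1 call for Fisher's exact test on each PT at the 5% level. Neither says whether the counts are of all AEs or of TEAEs.

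**Collection before treatment.** Under protocol 6.4.1, patients receive Hydrabak at selection to use "until the inclusion visit, as well as a daily log to write eventual concomitant treatments and adverse events". At D0 the log comes back and AEs are collected, ahead of randomisation in the listed order.

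**The concern.** All AEs and all TEAEs stand side by side in one list, so in this SAP the word AE cannot be shorthand for TEAE. A programmer following SAP 4.3, 7.7.1 and 9.1 would count wash-out events in the severity and serious tables and show them under the arm the patient was later given. That contradicts the evaluation rule in both documents.

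The safety objective is DM05 over 84 days of treatment, and during wash-out every patient uses saline. The anticipated device effects (protocol 4.2) include foreign body sensation, burning and blurred vision. Protocol 1.1 lists the same complaints as symptoms of dry eye. A wash-out complaint can therefore share a PT with a device effect, and counting both weakens the contrast between products. Leaving the Fisher event set unnamed also lets it be chosen after the arms are known.

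**Working it through.** **The plan's own figure.** The only planning calculation concerns the primary endpoint, and it reproduces. With margin 2, SD 2.5, one-sided 2.5% and 90% power, n per arm = 2 × (1.960 + 1.282)² × 2.5² / 2² = 32.8, so 33. The noncentral t calculation gives 34 (power 0.9015), which is the plan's 68 in total. 68 / 0.85 = 80, or 40 per arm. This point does not depend on it and does not change it. The arm size of 40 is used below.

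**Which summaries can contain a wash-out event.** The Safety population (SAP 7.1.2) needs randomisation and at least one dose.

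- Maximum severity, severe and serious AEs: yes, for any wash-out event in a patient later dosed.
- AEs leading to withdrawal: only if an event starts in wash-out, persists, and causes exit after dosing. A patient who leaves during wash-out is in no arm.
- Treatment-related AEs: rarely, because an event before the first drop would not normally be attributed to the device.
- The TEAE table: no.
- Fisher tests: undetermined.

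**Share of observation time.** From protocol 6.3.5, wash-out is 7 to 14 days and treatment 84 days.

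- 7 / (7 + 84) = 7.7%
- 14 / (14 + 84) = 14.3%
- With the ±7 day window on D84: 7 / (7 + 91) = 7.1% to 14 / (14 + 77) = 15.4%

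These are shares of days. The documents give no AE rates, so the share of events cannot be derived.

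**Illustration of dilution.** All rates here are assumptions. Let p be the chance that a patient reports a given PT on treatment, and w the chance of the same PT in wash-out, equal in both arms and independent of p. A table on all AEs then estimates 1 − (1 − p)(1 − w). The difference between arms shrinks only by the factor (1 − w), but the lower-rate arm moves away from zero and precision falls. Exact two-sided Fisher power at 40 per arm:

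| On-treatment rates | w = 0 (TEAEs) | w = 2.5% | w = 5% | w = 10% |
|---|---|---|---|---|
| 25% v 2.5% | 0.81 | 0.72 | 0.64 | 0.51 |
| 30% v 5% | 0.82 | 0.75 | 0.68 | 0.56 |
| 20% v 0% | 0.84 | 0.70 | 0.60 | 0.45 |

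Example: for 25% v 2.5% with w = 5%, the rates become 1 − 0.75 × 0.95 = 28.75% and 1 − 0.975 × 0.95 = 7.375%. The difference is 21.4 points instead of 22.5.

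**Single events.** Counts of 6 v 0 out of 40 give p = 0.026. One wash-out case added to each arm (7 v 1) gives p = 0.057. One added to the lower arm only (6 v 1) gives p = 0.108.

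**False positives.** With equal rates in both arms, the Fisher test rejects with probability 0.004 at a rate of 5% and 0.025 at 15%. Wash-out events that balance in expectation do not push it above its 5% level.

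**The case against.** The strongest case is that this is a loose end in wording with no decision attached. Success is defined by the Oxford score alone (protocol 7.4), and safety is summarised descriptively. A TEAE table by SOC, PT and arm is planned and answers the safety objective directly. The AE listings carry the D0 date and the event dates, so pre-treatment events stay identifiable. Showing all AEs beside TEAEs is a legitimate presentation. All of this stands, and it limits the weight of the point.

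Four stronger readings are tempting, and the documents do not support them.

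- *The Fisher tests are defined on all AEs.* They are not: the event set is unnamed. The general rule points to TEAEs, and a TEAE table exists to which the tests could apply. The gap is an ambiguity.
- *Only the overall table has a TEAE version.* The second block of SAP 7.7.1, which covers severity, relationship, seriousness and withdrawal, opens with a remark that ocular and non-ocular TEAEs are analysed separately. TEAE breakdowns of those categories may be intended. However, the items beneath are still labelled AEs, and SAP 9.1 lists no such tables.
- *Wash-out events bias the comparison for or against DM05.* Wash-out comes before randomisation and uses the same saline for everyone, so the events balance in expectation.
- *Some 8% to 14% of the counted events are pre-treatment.* That is a share of days. The tables count patients with at least one event, so a patient with the same PT in both periods counts once. Dryness symptoms are also rated separately at D0, D35 and D84, and whether they would be logged as AEs as well is unknown.

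None of this reconciles a rule limited to TEAEs with by-arm severity and serious tables that have no onset limit.

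**Conclusion.** The contradiction is real, and it lies within protocol 7.1.3 itself as well as between SAP 4.2 and SAP 4.3, 7.7.1 and 9.1. Followed as written, the plan puts wash-out events of later-dosed patients into the by-arm severity and serious summaries, touches the related and withdrawal summaries only marginally, and leaves the Fisher event set open.

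The consequence is dilution and chance imbalance in arms of 40. Systematic bias and an inflated false-positive rate are not shown. The power figures illustrate how few events matter; they rest on assumed rates, independence between periods, and the Fisher test being run on all AEs. The primary result and the sample size are unaffected. It is worth correcting because the remedy costs almost nothing.

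**What to change.** In protocol 7.1.3 and SAP 4.3, 7.7.1 and 9.1:

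- State that the by-arm severity, related, serious and withdrawal summaries and all Fisher tests use TEAEs in the Safety population. Add the treatment-emergent condition to the corresponding flags in SAP 4.3 and retitle the tables in SAP 9.1.
- Show AEs with onset before the first instillation in a separate listing or a wash-out table pooled over arms.
- Keep an all-AE overview if wanted, as description without tests.

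The TEAE definition in SAP 7.7.1, including its default for missing onset dates, can be used as it stands. The cost is wording in these four places and one filter on a definition already given. The protocol wording would follow the amendment route in protocol section 9. No data collection or sample size changes.
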